Unpublished data in adolescent with type 1 diabetes demonstrated a positive relationship between urine pH and urine uric acid (r=0.48, p<0.0001, n=99, **Figure 1**), suggesting increased solubility of urine uric acid with more alkaline urine.

Preliminary data from adolescents with type 1 diabetes in the *Determinants of Macrovascular Disease* cohort.

However, no data exist on whether urinary alkalinization by sodium bicarbonate can increase solubility of urine uric acid and reduce precipitation and crystallization thereby preventing tubular injury.

IV. Research Methods

A. Outcome Measure(s):

Urine uric acid concentration, precipitation and crystallization measured before and after sodium bicarbonate treatment to increase urine pH.

B. Description of Population to be Enrolled:

Inclusion criteria: In this study we will aim to recruit 78 adults, both males and females aged 18-60 years with type 1 diabetes. Assuming 80% of subjects approached will be eligible to participate and 60% of eligible subjects will consent to participate, this provides at least 47 subjects which is needed for power of 0.8 to detect effect size of 20% in change in urine uric acid.

- Participants must be able to be fasting prior to study visit #2 and #3 at CTRC
- Participants must be able to give informed consent.

Visit #1 will take place at Barbara Davis Center in association with the participants' regular diabetes visit. We plan to meet them before or after their regular visit to discuss study

details including the pre-study diet, review medical history to determine study eligibility and consent eligible and interested participants. This visit will determine eligible prior to diet, urine and blood collection and thereby minimize risk and participant burden. We will also obtain consent from eligible participants during this visit.

Exclusion Criteria:

- Non-type 1 diabetes
- History of eGFR <60 ml/min/1.73m² or albuminuria
- History of hypocalcemia or at risk of hypocalcemia (metabolic alkalosis increases binding of calcium to albumin causing a low ionized calcium which can in rare cases cause laryngospasms, paresthesia and seizures in those with already low calcium)
- Taking allopurinol or uric acid altering medications
- Ketogenic diet (secretory mechanisms for uric acid may be inhibited by lactate, betahydroxubutyrate and acetoacetate)
- Ketonuria (secretory mechanisms for uric acid may be inhibited by lactate, betahydroxubutyrate and acetoacetate)

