- Taking phosphorus binders (e.g. sevelamer)
- Taking blood pressure medications
- Taking SGLT2 inhibitors
- Pregnant or breastfeeding
- Taking the following medications which may interact with sodium bicarbonate (phentermine, pseudoephedrine, antifungal medication, cephalosporin antibiotics [e.g. Keflex], tetracycline antibiotics [e.g. doxycycline], steroids or lithium)

C. Study Design and Research Methods

Participants will be recruited from Diabetes Clinic at Barbara Davis Center. Informed consent will be obtained following standard COMIRB approved methods by the PI and/or members of the research team.

Sodium Bicarbonate Dose

- 3900mg (2x doses 1950 mg) of Sodium Bicarbonate over 24 hours was decided on based on the following:
 - Usual adult daily doses for Sodium Bicarbonate are 1,200-8,000mg with 1 gram providing 12 mEq (mmoL) each of sodium and bicarbonate.
 - For urinary alkalinization (with a goal urine pH of 8.0) doses tend to be greater and up to 12,000 mg daily (16).
 - We do not aim to alkalinize the urine of our participants (urine pH > 8.0) but rather normalize the relatively acidic urine found in participants with type 1 diabetes, by increasing the urine pH by 0.5 – 1.0.
 - Extrapolating from published urinary alkalinization data (16) and discussing with [name] we decided on approximately 4,000mg divided BID over 24 hours. Sodium Bicarbonate comes in 650mg tablet dosing which led to 1,950mg BID (3,900mg).

Recruitment

Participants will be recruited from Adult Diabetes Clinic at Barbara Davis Center by phone. We will discuss study details including the pre-study diet and fasting instructions. Interested participants will be mailed:

- Fasting instructions (for visit #1 and visit #2)– Patients will be asked to fast after midnight and will be asked to omit caffeine and smoking prior to the visit and
 - Fasting and insulin dosing instructions will be provided for the participants to reduce risk of hypoglycemia (these instructions are similar to what is provided once patients with type 1 diabetes come in for fasting labs)

- Participants will fast for only 8 hours
- Participants on insulin pump will be informed to not give themselves a bolus in the morning since they are fasting
- Participants on taking insulin by injections will be informed to not give themselves a bolus in the morning since they are fasting

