- Diet instructions (for visit #1 and visit #1) Patients will be asked to maintain a moderate protein (1.5g/kg of weight), and high sodium diet (3,450 mg of sodium per day) for one week prior to the study visit #1, and between study visit #1 and #2.
- Copy of patient information and consent form to review

Study Visit #1

Visit #1 will take place at Adult CTRC or Barbara Davis Center. Medical history will be reviewed and eligibility determined. . Informed consent will be obtained from eligible participants following standard COMIRB approved methods by the PI and/or members of the research team.

At this visit, participants will present fasting from midnight, height, weight and blood pressure will be measured. Urine will be collected and blood will be obtained via venipuncture by RN or venipuncture-trained PRA. The baseline blood will be drawn for serum uric acid, serum glucose, serum creatinine and serum cystatin C. Urine will be collected for urine pH, urine ketones, urine glucose, urine creatinine and urine uric acid. The urine will also be examined for precipitation and crystallization of urine uric acid. The participant will take 1950mg of sodium bicarbonate (3 x 650mg tablets) with water. We estimate that the study visit will take 60 minutes. After completion of the study visit, the participant will receive the second dose of sodium bicarbonate to take approximately 12 hours after the first dose (1950mg of sodium bicarbonate [3 x 650mg tablets]).

The participants will need to remain on the moderate protein and high sodium diet until completion of study visit #2. We will have provide protein bars, or participants may bring their own high protein snack.

Study Visit #2:

Visit #2 will take place at Adult CTRC or Barbara Davis Center. Participants will present fasting from midnight. Urine will be collected and blood will be obtained via venipuncture by RN or venipuncture-trained PRA. Blood will be drawn for serum uric acid, serum glucose, serum creatinine and serum cystatin C. Urine will be collected for urine pH, urine ketones, urine glucose, urine creatinine and urine uric acid. The urine will also be examined for precipitation and crystallization of urine uric acid.

D. Description, Risks and Justification of Procedures and Data Collection Tools:

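### Two visit schedules, offset by one visit: Section IV.C runs a one-week research diet before eligibility and consent, which Section IV.B places ahead of the diet

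*Combined protocol and SAP*

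**What the plan says.** **Section IV.B (Description of Population to be Enrolled).** Visit #1 is held at the diabetes clinic around the person's routine appointment. Staff explain the study and its diet, go through the medical history and settle eligibility. The stated reason is: "This visit will determine eligible prior to diet, urine and blood collection and thereby minimize risk and participant burden." It continues: "We will also obtain consent from eligible participants during this visit." The fasting criterion in the same section names visits #2 and #3, so this is a three-visit schedule.

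**Section IV.C (Recruitment; Study Visit #1; Study Visit #2).** Recruitment is by phone: "We will discuss study details including the pre-study diet and fasting instructions." Interested people are then mailed fasting instructions for visits #1 and #2, diet instructions, and a "Copy of patient information and consent form to review." The diet is a "high sodium diet (3,450 mg of sodium per day) for one week prior to the study visit #1", continuing until visit #2 is complete. At visit #1, "Medical history will be reviewed and eligibility determined" and "Informed consent will be obtained from eligible participants following standard COMIRB approved methods by the PI" or the research team. Baseline urine and blood and the first dose belong to that same visit. Visit #2 is the post-treatment collection, and no visit #3 is described.

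**Section IV.D (Compliance; Plan to minimize risk).** The first dose is given at visit #2, followed by at least one hour of monitoring.

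**The concern.** The order of eligibility review, consent and a study-imposed procedure is a basic protection, and the protocol answers the question in two ways. IV.B puts eligibility ahead of the diet and says this limits risk and burden. In IV.C, a person who agrees by phone could complete a week of research diet before anyone is required to compare their history with the exclusions, and before consent. Those exclusions include a past eGFR below 60 ml/min/1.73m² or past albuminuria, and "Taking blood pressure medications." Someone with one of these could finish a diet that the protocol itself calls high in sodium and only then be found ineligible.

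The numbering adds a practical problem. Staff working from IV.B, IV.C and IV.D could attach different procedures to the same visit number, including the first dose.

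**Working it through.** No sample size or power figure is involved, so the check sets the sections side by side.

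| Step | IV.B, with Compliance text in IV.D | IV.C |
|---|---|---|
| Eligibility review | Visit #1, before the diet | Visit #1, after the diet week |
| Consent | Visit #1, before the diet | Visit #1, after the diet week |
| Fasting visits | #2 and #3 | #1 and #2 |
| Baseline sampling | Visit #2 (implied by the first-dose visit) | Visit #1 |
| First dose | Visit #2 | Visit #1 |
| Post-treatment sampling | Visit #3 (implied; no procedures listed under that number) | Visit #2 |
| Numbered visits | 3 | 2 |

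1. **Offset.** Baseline sampling and first dose move from #2 to #1, and post-treatment sampling from #3 to #2. The shift is exactly one visit.

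2. **Is it only numbering?** No. If every visit number in IV.C were raised by one, IV.C would still describe eligibility and consent at the visit where samples are drawn and the first dose is taken, after the diet week. The order itself differs.

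3. **Does anything in IV.C place screening or consent before the diet?** The call is described as a discussion of study details, the mailed consent form is for review, and the consent sentence that opens IV.C gives no timing. The only eligibility and consent steps that IV.C places in time are at its visit #1.

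4. **Size.** Research-diet days before eligibility and consent: one week = 7 under IV.C, 0 under IV.B.

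5. **Before/after comparison.** In each schedule read alone, the first dose falls at the first of two fasting visits, after baseline sampling. The contrast is defined under both.

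6. **Smaller mismatches.** The diet instructions are labelled for visit #1 twice, although the same sentence goes on to name visits #1 and #2. Under IV.C's schedule, visit #1 is estimated at 60 minutes, while IV.D requires at least 60 minutes of monitoring after the first dose. That leaves 60 − 60 = 0 minutes for history, consent, measurements and sampling.

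7. **Number of people affected.** None is claimed. The recruitment figures in IV.B give no safe base: 78 × 0.80 × 0.60 = 37.4, whereas the stated 47 matches only 78 × 0.60 = 46.8.

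**The case against.** The best reply is that the conflict is narrow and mostly clerical. Several parts of it stand.

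- IV.B protects three things: diet, urine collection and blood collection. In IV.C, eligibility and consent still come before urine, blood and the first dose. Only the diet is out of order.
- The link between the diet and the renal and blood-pressure exclusions is an inference. The protocol does not draw it, does not list the diet among the risks to be minimised, and does not give usual sodium intake, so the change in exposure is unknown.
- The fasting and insulin instructions, also mailed before visit #1, are described as similar to those for routine fasting labs, so they add little to the concern.
- The visit numbers can be mapped onto each other. The duplicated visit #1 label is a slip, and the 60-minute mismatch sets an estimate against a minimum.

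It can also be said that the consent documents and submission forms are not in the text reviewed, and might contain an earlier screening step. That limits what can be said about intent. It does not remove the contradiction: IV.B and IV.C both stand in the same dated version and give opposite orders for the diet.

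**Conclusion.** The concern holds. IV.B puts eligibility and consent before the diet; IV.C as written puts 7 days of diet before both. This must be corrected, because IV.C undoes, for the diet, a protection that IV.B states and explains. The conclusion rests on the current protocol text alone, on reading the phone call and the mailed form as no more than what is written, and on consent in IV.B preceding the diet because it is taken at the same visit as the eligibility review.

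The numbering conflict (three visits against two, first dose at #2 or #1) follows from the same offset and would be minor alone, as would the 60-minute mismatch. No effect on the outcome comparison, the analysis or the power is claimed, and no harm from the diet has been quantified.

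**What to change.** Reconcile IV.B, IV.C and IV.D to one numbered visit schedule, ideally as a short table. It should:

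- state at which contact or visit each of these falls: eligibility review, consent, start of diet, pre-dose sampling, first dose, monitoring and post-dose sampling;
- settle the order of eligibility and consent relative to the diet, checked against the purpose given in IV.B;
- say whether a visit #3 exists and, if so, what happens there;
- use the same visit numbers in the IV.B fasting criterion, the mailed fasting and diet instructions, and the Compliance paragraph;
- bring the visit-length estimate into line with the minimum monitoring hour.

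The cost is protocol text, with no added participants, samples or assays. If a separate eligibility and consent contact is kept, IV.B already describes one alongside the regular diabetes appointment.

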In any clinical study unforeseen human factors provide challenges. The current study is based upon a previous study with sodium bicarbonate administration in adults with no reported adverse effects. Furthermore, we aim to use lower doses of sodium bicarbonate in this study. We have also performed careful power analyses to allow meaningful analyses.

F. Data Analysis Plan:

(A HIPAA compliant, Red Cap database system will be used for this study.)

| Outcome | Effect size | SD pre and post | Correlation of pre with post | SD of change | Power | Ν |
|--------------------|-------------|--------------------|------------------------------------|-----------------|-------|----|
| Urine pH | 0.5* | 0.42 | 0.5 | 0.42 | >99 | 20 |
| | 1.0* | 0.42 | 0.5 | 0.42 | >99 | 10 |
| Urine uric acid | 10% | 16.48 | 0.95 | 5.21 | 80 | 47 |
| | 20% | 16.48 | 0.80 | 10.42 | 80 | 47 |

Table 1 Power calculations:

* Units on the pH scale

Per our power analysis, with a sample size of 50 we will have power of 0.8 to detect effect size of 20% change in urine uric acid following 24-hours of NaHCO₃. Paired t-test will be employed to evaluate whether the change in urine uric acid pre- and post NaHCO3 administration is statistically significant. We will also adjust for covariates with ANCOVA or linear regression models [ANCOVA vs. linear regression models will be decided based on the variation of urine uric acid at baseline in our participants].

We will also calculate fractionated excretion of uric acid (FeUA = [(UUA * SCr / SUA * UCr)*100]), and regress FeUA, SUA and UUA on eGFR calculated by CKD-EPI creatinine and cystatin C. Furthermore, we will also regress blood glucose and urine glucose on FeUA, SUA and UUA.

G. Summarize Knowledge to be Gained:

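### Does Table 1 overstate power for a 10% change in urine uric acid by giving that row a higher pre-post correlation?

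*Combined protocol and SAP*

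**What the plan says.** Table 1 in section IV.F (Data Analysis Plan) has two rows for urine uric acid:

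- the 10% change: "10% | 16.48 | 0.95 | 5.21 | 80 | 47"
- the 20% change: "20% | 16.48 | 0.80 | 10.42 | 80 | 47"

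After the effect size, the entries are the pre and post SD, the pre-post correlation, the SD of the change, the power and N. The plan gives no source for either correlation and does not label the rows as scenarios.

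Two sentences in the text use the table. Section IV.B refers to "47 subjects which is needed for power of 0.8 to detect effect size of 20% in change in urine uric acid". Section IV.F says "with a sample size of 50 we will have power of 0.8 to detect effect size of 20% change in urine uric acid". Both concern the 20% change, and neither mentions the correlation. No sentence claims power for 10%.

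The urine pH rows of the same table, "0.5* | 0.42 | 0.5 | 0.42" and "1.0* | 0.42 | 0.5 | 0.42", keep one correlation for both effect sizes but use different N (20 and 10). The planned test is a paired t-test. Alpha, sidedness and the baseline mean of urine uric acid are not stated.

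**The concern.** Both rows describe one outcome in one group of participants at the same two visits, so the trial will have a single pre-post correlation. A table that credits the same 47 participants with 80% power for an effect and for half that effect invites the suspicion that the correlation was adjusted until the power came out right. The pH rows, which hold the correlation fixed, strengthen that impression.

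What would be at stake is how a null result is read. If the true correlation is 0.80, a real 10% change would be missed about 7 times in 10. Someone who took the 10% row at face value would expect to miss it 2 times in 10, and might treat a non-significant test as evidence against a 10% change.

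**Working it through.** **Inputs.** From Table 1: SD 16.48 before and after, correlations 0.95 and 0.80, N = 47, power 80%. Assumed, because not stated: alpha 5%, run two-sided and one-sided. The baseline mean is not needed, because the calculation is calibrated to the table's own 80%.

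**Step 1: reproduce the printed SDs of change.** SD of change = SD × √(2(1 − r)).

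- r = 0.95: 16.48 × √0.10 = 5.21, as printed.
- r = 0.80: 16.48 × √0.40 = 10.42, as printed.

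**Step 2: why the powers are equal.** Power in a paired t-test depends on effect ÷ SD of change, for a given N and alpha. The effect doubles from 10% to 20% and the SD of change doubles from 5.21 to 10.42, so the ratio is unchanged (10/5.21 = 20/10.42). Equal power follows for any baseline mean and any alpha. Both rows also imply the same baseline mean when solved backwards from 80%: 21.75 two-sided or 19.18 one-sided. The rows therefore agree with each other.

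**Step 3: the 10% change at r = 0.80.** With the noncentral t distribution and n = 47, 80% power needs a standardized effect of 0.4174 (two-sided) or 0.3681 (one-sided). Keeping the 10% change but using the SD of change for r = 0.80 halves these to 0.209 and 0.184.

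- Two-sided 5%: power about 29%. If the printed 80 is a rounding of anything from 79.5 to 80.5, the range is 28.6% to 29.2%.
- One-sided 5%: power about 34%.
- N for 80% power would be 183 (two-sided) or 184 (one-sided).

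**Step 4: the claim made in the text, a 20% change at r = 0.80.**

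- N = 47: 80%, as stated.
- N = 50: 82%, on either sidedness.

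The different N in the two sentences does not harm the claim.

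**Step 5: read the rows as scenarios.** At N = 47 and 80% power, the detectable change is 20% × √((1 − r)/0.20), whatever the alpha or mean:

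| r | Detectable change |
|---|---|
| 0.95 | 10% |
| 0.90 | 14.1% |
| 0.85 | 17.3% |
| 0.80 | 20% |
| 0.70 | 24.5% |

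The two printed rows are the first and fourth lines of this table.

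**The case for a change.** The case for a change is that Table 1 is the only quantitative support for the sample size, yet it switches an unsourced assumption within one outcome without comment. The two power sentences are worded without conditions, although the 20% claim depends on the correlation: at N = 47 and two-sided 5%, its power is 98% at r = 0.90 but 63% at r = 0.70. Being a pilot is no full answer, since a significance test is planned. The remedy would cost one label and a clause in two sentences.

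The facts in this case stand. The correlations have no stated source, and the 10% row fails at r = 0.80. Three things limit their weight.

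- The condition is not hidden. The correlation has its own column, filled in on every row, with the resulting SD of change beside it. The 10% row cannot be read in full without meeting its 0.95.
- The pH rows set no rule that only the effect size may vary, because they change N between rows.
- The misreading of a null result is the reader's and not the plan's. The plan has no futility, equivalence or go/no-go rule tied to a 10% change.

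The true correlation cannot be settled from the documents. Both visits are fasting, and "participants will need to remain on the moderate protein and high sodium diet until completion of study visit #2". Those features would tend to raise the correlation, but they give no value. Replacing the printed 80 in the 10% row with 29 would swap a figure that is correct on its own inputs for one that rests on an alpha the plan does not state.

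**Conclusion.** No change is called for. The suspicion is reasonable and its arithmetic is right: at r = 0.80 and N = 47, power for a 10% change is about 29% assuming two-sided 5%, or 34% assuming one-sided 5%. But the plan never claims 80% power for that combination. Each row is correct at its own printed correlation, rows with different correlations at a fixed N read naturally as alternative scenarios, and the text relies only on the 20% change.

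That 20% claim rests on a correlation of at least 0.80 and on 47 participants actually being obtained. Whether the recruitment rates in IV.B yield 47 is a separate question, not settled here.

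Marking the rows as detectable changes under two correlations, and calling those correlations assumptions, would be a courtesy to the reader. It would write down a condition the table already shows and would leave enrolment, the analysis and every decision as they are.

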COMIRB Protocol

COLORADO MULTIPLE INSTITUTIONAL REVIEW BOARD [name] [contact] [contact]

Protocol #:15-0541Project Title:Effect of Urinary Alkalinization on Urine Uric Acid Precipitation and
Crystallization in Adults with Type 1 Diabetes

Principal Investigator: [name]. Version Date: 6/24/16

I. Hypotheses and Specific Aims: A brief statement of the purpose of the research project. This section should include the hypotheses and specific aims being tested in the research. *Note: If you are applying for QA/QI/PE determination, you should not use terms like "hypothesis" or "research;" Instead, use the terms "aims" or "goals" and "evaluation."*(Approx. 1 paragraph)

| Specific Aim 1: | To evaluate the ability of 2 doses of oral sodium bicarbonate (1950mg each) to alkalize urine over 24 hours in adults with type 1 diabetes and without chronic kidney disease. |
|------------------------|--|
| Hypothesis 1: | Sodium bicarbonate over 24 hours can increase urine pH by 0.5-1.0 in adults with type 1 diabetes and without chronic kidney disease. |
| Specific Aim 2: | To evaluate the effect of urinary alkalinization on urine uric acid concentration, precipitation and crystallization in adults with type 1 diabetes and without chronic kidney disease. |
| Hypothesis 2: | Increasing urine pH with oral sodium bicarbonate in adults with type 1 diabetes and without chronic kidney disease will solubilize urine uric acid thereby increasing urine uric acid, decreasing urine acid precipitation and crystallization |
| Specific Aim 3: | To evaluate the relationship between urine uric acid concentration, precipitation and crystallization with glomerular function and markers of tubular injury in adults with type 1 diabetes and without chronic kidney disease. |
| Hypothesis 3.1: | Urine uric acid concentration, precipitation and crystallization will be associated with markers of tubular injury (e.g. NGAL, MMP9) in adults with type 1 diabetes and without chronic kidney disease. |
| Hypothesis 3.2: | Urine uric acid concentration, precipitation and crystallization will be associated with estimated glomerular filtration rate (CKD-EPI creatinine and cystatin C) in adults with type 1 diabetes and without chronic kidney disease. |

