Serum uric acid (SUA) is lower in adolescents and adults with type 1 diabetes compared to non-diabetic peers (4, 5). Despite lower levels SUA remains an important risk factor for diabetic nephropathy in type 1 diabetes (6), with a large clinical trial underway examining the ability of allopurinol to prevent early renal loss (7). Several mechanisms have been proposed to explain the lower levels of SUA in type 1 diabetes including glucosuria induced uricosuria leading to spilling of urine uric acid (UUA) and lowering of SUA (8), and the notion that intracellular uric acid (IUA) and/ or UUA rather than SUA may be responsible for the development of complications. Animal studies have demonstrated that blocking uric acid production protects the kidney from tubulointerstitial injury, which suggests a causal role for uric acid in the development of diabetic tubular injury (9, 10). Relative dehydration, secondary to glucosuria, exercise or inadequate liquid intake, may lead to concentrated and acidic urine, which may cause UUA to precipitate and crystallize in type 1 diabetes (11-14). The UUA precipitation and crystallization is thought to induce inflammation and injury of the tubules with possible retrograde glomerular injury (11-14). Moreover, it was recently shown that UUA promoted apoptosis in human proximal tubular cells by oxidative stress and activation of NADPH Oxidase NOX 4 (15).

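### The named pre/post test of urine uric acid is on a concentration with no dilution adjustment specified, so it cannot on its own attribute a change to solubilisation, although urine creatinine is measured at both visits

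*Combined protocol and SAP*

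**What the plan says.** Section IV.A declares the outcome: "Urine uric acid concentration, precipitation and crystallization measured before and after sodium bicarbonate treatment to increase urine pH". Hypothesis 2 in Section I gives the expected mechanism, that raising urine pH "will solubilize urine uric acid thereby increasing urine uric acid". Section IV.F names the test: "Paired t-test will be employed to evaluate whether the change in urine uric acid pre- and post NaHCO3 administration is statistically significant". It adds covariate adjustment by ANCOVA or linear regression, but names no covariates.

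Under both Study Visit #1 and Study Visit #2 in Section IV.C, the plan states: "Urine will be collected for urine pH, urine ketones, urine glucose, urine creatinine and urine uric acid". The only stated analytic use of urine creatinine is the fractional excretion of uric acid (FeUA). The plan will "regress FeUA, SUA and UUA on eGFR calculated by CKD-EPI creatinine and cystatin C" and also relate these quantities to blood and urine glucose. It does not compare FeUA before and after treatment. No timed collection, urine volume, specific gravity or rule on fluid intake is stated.

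**The concern.** Hypothesis 2 is a claim about solubility, but a concentration also moves with the amount of water in the urine. The Background section recognises this: "Relative dehydration, secondary to glucosuria, exercise or inadequate liquid intake, may lead to concentrated and acidic urine". Pairing removes stable differences between people. It does not remove a shift shared by most participants at the second visit, and without a control arm nothing else in the design does. A rise, a fall or a null result could then be read as evidence for or against solubilisation when part of it is dilution. The measurement that would allow a check, urine creatinine from the same sample, is already collected.

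**Working it through.** **Inputs from Table 1 (IV.F), 20% row for urine uric acid:** SD 16.48 before and after, correlation 0.80, SD of change 10.42, power 80%, N=47. The documents give no baseline mean, significance level or sidedness; two-sided 0.05 is assumed.

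**Step 1, reproduce the plan.** SD of change = SD × √(2(1−r)) = 16.48 × √0.40 = 10.42. The 10% row gives 16.48 × √0.10 = 5.21. Both match. N=47 cannot be checked independently without the baseline mean. Back-solving (noncentral t, 46 df, 80% power) gives a standardised effect of 0.4174. The detectable change is 0.4174 × 10.42 = 4.35, so the mean is 4.35/0.20 = 21.75. The 10% row implies the same mean.

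**Step 2, add an assumed dilution shift.** If the second urine is more dilute by a fraction q, the apparent change is (1 + effect)(1 − q) − 1. Multiply by 21.75 and divide by 10.42 for the standardised effect.

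| True effect | Assumed shift | Apparent change | Significant rise | Significant fall |
|---|---|---|---|---|
| +20% | none | +20% | 80% | <0.5% |
| +20% | 5% more dilute | +14% | 50% | <0.5% |
| +20% | 10% more dilute | +8% | 20% | <0.5% |
| none | none | 0 | 2.5% | 2.5% |
| none | 5% more dilute | −5% | <0.5% | 10% |
| none | 10% more dilute | −10% | <0.5% | 29% |
| none | 5% more concentrated | +5% | 10% | <0.5% |
| none | 10% more concentrated | +10% | 29% | <0.5% |

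With the N of 50 given in the text, the first three powers are 82.5%, 53% and 21%.

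**Step 3, what a creatinine ratio would do.** This needs a model. Assume lognormal data with Table 1's SD and correlation:
- CV = 16.48/21.75 = 0.758
- log-SD = √ln(1 + 0.758²) = 0.674
- log correlation = ln(1 + 0.80 × 0.758²)/ln(1 + 0.758²) = 0.833
- within-person log-SD w = 0.674 × √(1 − 0.833) = 0.275

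Also assume that dilution makes up f = 25% of within-person log variance, and that creatinine excretion has log-SD c = 0.15. Then:
- SD of change in log concentration = w√2 = 0.389
- SD of change in log ratio = √(2w²(1 − f) + 2c²) = 0.398

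For a true 20% rise (ln 1.2 = 0.182), N=47 and no shift, power is 88% on log concentration and 87% on the log ratio. Simulation gives 74% on raw concentration. That is below Table 1's 80% because a multiplicative rise widens the SD of change to 11.9.

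In simulation with a true 20% rise and 10% dilution, the raw test detects the rise 20% of the time and the ratio 87%. With no effect and urine 10% more concentrated, a false rise appears 28% of the time on raw concentration and 2.6% on the ratio.

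**Step 4, the ratio's own weakness.** If creatinine excretion is 5% or 10% higher at the second visit (assumed), the log effect falls to 0.182 − 0.049 = 0.134 or 0.182 − 0.095 = 0.087. Dividing by 0.398, power is 61% or 31%. With no effect, a false fall appears 13% or 36% of the time. With f = 0 and c = 0.20, the SD of log change is 0.481 and no-shift power is 72%. With f = 0.5 and c = 0.10, they are 0.309 and 98%.

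**The case against.** Several points on the other side stand.

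- **The test matches the declared outcome.** Aim 2 and Section IV.A name concentration, and the Background treats concentrated, acidic urine as part of the route to precipitation. A reader might infer that the paired t-test is invalid or that a ratio should replace it. The documents support neither.
- **Creatinine is not ruled out.** A reader might infer that the plan excludes any creatinine correction. It does not: covariates are unnamed, and FeUA is itself creatinine-corrected. What can be said is that no dilution adjustment is specified for the pre/post comparison.
- **No shift is shown.** Both urines follow an overnight fast without caffeine, on the same diet. Random dilution noise does not bias a paired test. One might infer that treatment itself dilutes the second sample, because "The participant will take 1950mg of sodium bicarbonate (3 x 650mg tablets) with water" and the two doses carry 3.9 g × 12 mEq/g = 46.8 mEq of sodium (IV.C: "1 gram providing 12 mEq (mmoL) each of sodium and bicarbonate"). But the second sample follows a further overnight fast, and nothing in the documents links that water or sodium to dilution in it. This route is speculative.
- **Creatinine correction is not shown to gain precision.** Setting 74% (raw) beside 87% (ratio) suggests that it does. The gain comes from the log scale, since log concentration alone gives 88%. With c = 0.15, the ratio is the less noisy only if dilution exceeds 0.15²/0.275² = 30% of within-person log variance.
- **The ratio replaces one assumption with another.** Creatinine drift does about as much harm to the ratio as an equal dilution shift does to the concentration test. The documents do not show which would be larger.

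None of this lets the concentration test alone separate solubilisation from dilution. Similar conditions at both visits make a shift less likely but do not exclude one.

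**Conclusion.** The point holds as a limit on interpretation, not as an error in the named test. The paired t-test answers whether concentration changed. It cannot alone say why, and the plan specifies no analysis that would help, although the data for one are collected. The possible size is material: modest assumed shifts of 5% to 10% take power for a true 20% rise from 80% to 50% or 20%, or give a significant result in the shift's direction 10% or 29% of the time when nothing has happened.

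These figures rest on assumed shifts, a back-solved mean, N=47 and an assumed two-sided 0.05. The ratio figures also rest on the lognormal model and on assumed values for dilution and creatinine variability. Because no shift is documented, this is a worthwhile, inexpensive addition to a pilot, held with medium confidence.

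**What to change.** Change the wording of Section IV.F only:

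1. Keep the concentration outcome and its paired t-test as the named test.
2. Pre-specify one supporting analysis: a paired t-test on log(UUA/UCr), where UUA is urine uric acid and UCr is urine creatinine. Give it as a geometric mean ratio with 95% CI, and report it whatever its significance.
3. State that a change in concentration will be attributed to solubilisation rather than dilution only as far as the log(UUA/UCr) estimate and its CI support it. State also that the ratio is not a second route to declaring success. Under the model above, letting either test count would raise the false-rise rate from 2.4% to 4.2%. Do not require both to be significant: at 10% dilution that leaves 20% power.
4. If FeUA is also compared before and after, report it descriptively and write it as (UUA × SCr)/(SUA × UCr) × 100, where SCr is serum creatinine and SUA serum uric acid. As printed, UCr could be read as multiplying, so dilution would not cancel.
5. Claim no precision gain from creatinine correction.

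All four measurements are already taken at both visits, so there is no added sample or visit. The cost is interpretive: the ratio assumes stable creatinine excretion, and it does not remove true changes in uric acid excretion, such as the glucosuria-driven uricosuria described in the Background. Both limits should be stated beside the result.
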